6.4. Sample Size Determination

The sample size for this cluster randomized trial is determined using standard approaches for cluster-randomized trials with proportion (binary) outcomes, aligned with Hayes and Bennett (1999). This study specifically screens individuals with known chronic conditions, the primary endpoint is evaluated as the proportion of chronic patients identified as requiring palliative care.

The calculation is based on estimating the difference in identification proportions between the intervention and control arms. Based on literature, we estimate the baseline identification proportion of palliative care needs among chronic patients in routine care P1 to be 5% (0.05). We hypothesize that the DINKNESH App will increase systematic identification by a factor of 3, resulting in an expected proportion (P2) of 15% (0.15) in the intervention arm.

To detect this difference with 85% power ($Z_{1-\beta} = 1.04$) and a 5% significance level ($Z_{1-\alpha/2} = 1.96$), we calculated the unadjusted sample size and then applied a Design Effect (DE) to account for facility-level clustering. We estimated an ICC of 0.03, supported by methodological standards for primary care practice-level clustering.

Each cluster is defined as two Family Health Team (FHT). Based on routine service data, two FHT encounters approximately 120 individuals that have underlying chronic conditions over a six-week period. Thus, the expected average cluster size (m) of eligible chronic patients over the six-week study period is 120.

Then, the required design effect is 4.57. Multiplying the unadjusted individual sample size (approximately 157.5 per arm) by this design effect requires approximately 720 chronic patients per arm. Dividing this by the average cluster size ($m = 120$) yields exactly 6 clusters per arm. This results in a total of 12 clusters included in the study. This provides a total expected denominator of 1,440 routine chronic patient encounters over the six-week study period.

$$n = (Z_{1-\alpha/2} + Z_{1-\beta})^2 \times (p_1(1-p_1) + p_2(1-p_2)) \times (1 + (m-1)\rho) / (p_1 - p_2)^2 \times m$$

- ($Z_{1-\beta} = 1.04$) and a 5% significance level ($Z_{1-\alpha/2} = 1.96$)
- Baseline identification proportion (P1): 0.05 (5%)
- Expected identification proportion (P2): 0.15 (15%)
- Difference in proportions: 0.1
- Average chronic patient encounters per cluster (m): 120 (over 6 weeks)
- Design Effect (DE): $1 + (m-1) \times ICC = 1 + (119 \times 0.03) = 4.57$
- Clusters per arm (c): 6 (12 total)
- Total N= 1440

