6.5. Sampling Method

In this study, we will use multistage sampling aligned with the principles of a cluster randomized controlled trial. In the first stage, the clusters are health centers within Addis Ababa that have palliative care services through Family Health Teams. Of the 101 health centers, 95 currently deliver palliative care and will form the sampling frame. A complete list of eligible facilities will be obtained from Addis Ababa regional health bureau. To make sure the selected clusters are representative of the city, we will use stratified random sampling, stratifying facilities by patient volume. After this, these facilities will be randomly allocated to either the intervention or control group using a computer-generated sequence managed by an independent person so that there's allocation concealment. A total of 12 clusters (6 per arm) will be included in the study.

In the second stage, all patients currently diagnosed with a chronic illness and receiving follow-up home-visit care from the Family Health Teams within the selected cluster

catchment areas will be included consecutively. This population forms the denominator for the study's proportion-based primary outcome, representing the total reach of the implementation environment. Given that the screening is integrated into routine clinical care, verbal informed consent will be sought from each identified patient (or their proxy caregiver) for the research use of their data. This verbal consent will be witnessed and documented. The numerator will then be defined as the subset of these chronic patients who are successfully screened and identified for palliative care needs using either the DINKNESH App (intervention) or standard paper-based tools (control). This multistage approach ensures that the study captures real-world implementation fidelity while minimizing selection bias among the target chronic patient population.

For the qualitative component, we'll purposely identify healthcare providers and key stakeholders from facilities assigned to the intervention arm. Participants will be chosen based on their direct involvement in the rollout or oversight of the palliative care App, ensuring diversity across roles. Data will be collected through FGD organized by professional category to foster open dialogue and reduce hierarchical influence. The number of FGDs will be guided by thematic saturation, typically reached after four to six FGDs.

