6.8. Data Analysis

We will have a mixed-methods design, analyzing quantitative and qualitative data separately and then integrating the findings during interpretation to generate a comprehensive understanding of the DINKNESH App's effectiveness and Implementation.

The primary effectiveness outcome for analysis is defined as the number of patients identified as having palliative care needs by family health teams during routine home visits over 6 weeks study period. This outcome will be operationalized as the number of individuals identified as requiring palliative care divided by the total number of chronic patient encounters conducted within each cluster.

In alignment with the study objectives, quantitative analyses will address the identification of patients with palliative care needs (primary outcome)

Quantitative data will be cleaned up and analyzed using standard statistical software Stata. Models with adjustment for clustering at the facility level will be used. This approach accounts for the clustered study design and enables valid comparison of identification rates between intervention and control arms. The model will test if the DINKNESH App process led to a significantly higher rate of patient identification and documented action compared to the Control arm.

For the Qualitative part, We will analyze the transcripts from the Focus Group Discussions using thematic analysis. This involves systematically reading the transcripts and categorizing recurring quotes and ideas into specific themes. This analysis will tell us the exact process issues that need fixing before the DINKNESH App can be scaled up

nationally.

Findings from quantitative analyses will be triangulated with qualitative insights from healthcare workers and identified patients with palliative care need to contextualize observed differences in identification and clinical action, and to explain how and why the DINKNESH App influenced routine care practices.

7. Ethical Consideration

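### The 85% power in section 6.4 rests on normal quantiles; with 6 clusters per arm, a valid 5% test on 10 degrees of freedom has about 77–79% power on the plan's own inputs

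*Protocol*

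**What the plan says.** Section 6.4 plans the trial "To detect this difference with 85% power" "and a 5% significance level", and gives the two quantiles as 1.04 and 1.96. The proportions are 5% in control and 15% under the App. On clustering it says "We estimated an ICC of 0.03"; with an average of 120 chronic patients per cluster this gives a design effect of 4.57. An unadjusted 157.5 per arm becomes about 720 per arm, and dividing by 120 "yields exactly 6 clusters per arm", so 12 clusters and 1,440 patients in all. The calculation uses no t quantile, degrees-of-freedom adjustment or additional cluster.

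Section 6.8 says "Models with adjustment for clustering at the facility level will be used" and that this makes the comparison of the arms valid. It names neither the model nor the reference distribution for the test.

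**The concern.** Normal quantiles are right when the standard error of the treatment difference is known, or is estimated from many independent units. Here the independent units are the clusters. Six per arm leave 2 × (6 − 1) = 10 degrees of freedom for the between-cluster variance, so a test that keeps the 5% level needs a critical value of 2.228 instead of 1.96. The required number of clusters came out at 5.998 and was met with 6, so there is no slack to absorb the difference.

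At stake is how a null or borderline result would be read. The trial is meant to inform national scale-up of the App. A reader who trusts section 6.4 would think a true threefold increase had a 15% chance of being missed, when on the plan's own assumptions that chance exceeds 20%.

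**Working it through.** **Inputs (all from section 6.4).** p1 = 0.05, p2 = 0.15, two-sided 5% (1.96), 85% power (1.04), ICC = 0.03, m = 120, 6 clusters per arm. Cluster sizes are taken as equal, as the plan's design effect implies.

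**1. The plan's own figure.**
- Variance term: 0.05 × 0.95 + 0.15 × 0.85 = 0.0475 + 0.1275 = 0.175.
- Unadjusted n per arm: (1.96 + 1.04)² × 0.175 / 0.10² = 9 × 0.175 / 0.01 = 157.5.
- Design effect: 1 + 119 × 0.03 = 4.57.
- Per arm: 157.5 × 4.57 = 719.8. Clusters: 719.8 / 120 = 5.998, rounded to 6.
- With 6 clusters: SE = √(0.175 × 4.57 / 720) = 0.0333, so the standardised effect is 0.10 / 0.0333 = 3.00.
- Normal power: Φ(3.00 − 1.96) = 85.1%.

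The stated figure reproduces.

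**2. The same effect and standard error, tested on 10 degrees of freedom.**
- Critical value t(0.975; 10) = 2.228.
- Power from the non-central t distribution, non-centrality 3.00, 10 df: 77.2%.
- Normal approximation with the t critical value, as a rough check: Φ(3.00 − 2.228) = 78.0%.

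**3. Simulation check.** Beta-binomial clusters, ICC 0.03 in both arms, 120 patients per cluster, 200,000 simulated trials, t-test on the 12 cluster proportions:
- Power at 5% versus 15%: 79%.
- Type I error with equal proportions of 5%, 10% or 15% in both arms: 4.5–5.0%, so this test holds its level.

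**4. What 85% power would detect.** Replace p2 by 0.164:
- Variance term: 0.0475 + 0.164 × 0.836 = 0.1846.
- SE = √(0.1846 × 4.57 / 720) = 0.0342; non-centrality 0.114 / 0.0342 = 3.33.
- Non-central t power on 10 df: 85.0%.

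**5. What happens if 1.96 is kept.** Type I error when no small-sample correction is made:

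| Test, uncorrected for few clusters | Type I error |
|---|---|
| 1.96 applied to cluster summaries (t on 10 df beyond 1.96) | 7.8% |
| Random-intercept logistic, likelihood-ratio test | about 8% |
| Robust logit Wald z with a G/(G − 1) factor (G = number of clusters), equal sizes | 9.4–10.5% |
| Raw sandwich logit Wald z, equal sizes | 10.7–12.0% |
| Random-intercept logistic, Wald z | about 12–13% |
| Raw sandwich logit Wald z, assumed cluster-size CV 0.3–0.5 | 11.4–14.0% |

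All rows but the first are simulated; the mixed-model rows are approximate, because about 1–2% of those fits did not optimise cleanly. With 1.96 on cluster summaries, simulated power is close to the stated 85% (about 86%), but the test no longer runs at 5%.

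**The case against.** **The arithmetic is correct.** That stands. What fails is the approximation behind it, which is too generous with 12 clusters.

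**The ICC matters more than the reference distribution.** This also stands. With the same 10-df calculation, power is 88% at an ICC of 0.02, 86% at 0.022 and 67% at 0.04. Covariate adjustment might recover some precision, although each degree of freedom it uses costs a little (76.1% at 9 df, 74.8% at 8 df, before any gain). So 85% is not out of reach for this trial in every circumstance. But section 6.4 attaches 85% to an ICC of 0.03 with no adjustment, and on those inputs it does not hold.

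**A reader might infer that the planned analysis will have an inflated false-positive rate.** The protocol does not support that. Section 6.8 commits to no z test, Wald test or uncorrected sandwich estimator. It defines the outcome as a proportion within each cluster, which suits a cluster-level t-test, and the choice of correction may sit in a statistical analysis plan that is not shown. No single figure would apply anyway: the range is about 8–14% depending on the test.

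**A reader might also infer unequal cluster sizes from section 6.5**, which speaks of "stratifying facilities by patient volume". That does not follow. Section 6.4 defines a cluster as two Family Health Teams seeing about 120 chronic patients, so facility volume is not cluster size, and section 6.5 gives representativeness as the reason for stratifying. If sizes do vary, power falls. With a CV of 0.3–0.5, which is purely an assumption, the inflated design effect gives 74–70% and simulation gives 78–76%. The protocol gives no figure for this.

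**Conclusion.** The stated 85% power is overstated by about 6–8 percentage points. On the plan's inputs, a valid two-sided 5% test has about 77% power (non-central t) to 79% (simulated cluster-level t-test), and the difference detectable at 85%, by non-central t, is about 5% versus 16.4%. This rests on an ICC of 0.03 in both arms, 120 patients in every cluster, 6 clusters per arm and no covariate adjustment. It does not depend on any assumption about unequal sizes.

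A missing analysis plan does not remove the point, because the power is a finished numerical claim in the protocol. If a valid small-sample test is specified, 85% is too high; if an uncorrected large-sample test is used, the 5% level is lost. The second branch is a conditional risk and not an error in the document.

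**What to change.** - **Section 6.4:** keep 12 clusters. Restate the power for 5% versus 15% as about 77–79% with a 10-df test, or keep 85% and restate the detectable difference as about 5% versus 16.4%. Add that power falls if cluster sizes vary.
- **Section 6.8:** state that the primary comparison uses a small-sample reference, either a t-test on the 12 cluster proportions with 10 degrees of freedom or a clustered model with a small-sample correction to its degrees of freedom and standard error. This secures the 5% level that section 6.4 assumes.

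The cost is a few sentences and a less favourable stated power; no patients or clusters are added. For information, if the sponsor prefers to recover the power, 7 clusters per arm would give about 84.5% by the same non-central t calculation (12 df), at the price of two more health centers.

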6.1. Study Setting

The study will be conducted in Addis Ababa, Ethiopia, targeting primary healthcare facilities within the city's administration. The sampling frame for this study consists of the 95 health centers currently reporting functional palliative care service delivery out of the 101 total health centers in the city. From this pool, 12 eligible health centers are selected to serve as the study clusters.

The research will leverage the existing Family Health Team (FHT) structure attached to these health centers. These teams are officially mandated to conduct systematic home-based visits within their respective catchment areas to provide a range of community-based health services.

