6.3.2. Study Population

Quantitative arm:

- Adult patients with chronic illnesses who are encountered by HCWs under the family health team during the active comparison period in facilities randomized to either the Intervention or Control group, and who meet the inclusion criteria.

Qualitative arm:

Health care workers:

- Health care workers who directly engaged in palliative care patient identification and who are also available for FGDs

Inclusion Criteria

- For patients(Quantitative Part):

- Adults aged 18 years or older
- Currently diagnosed with one or more chronic conditions and receiving home-based follow-up care from a participating Family Health Team within the catchment area of a selected study cluster
- Willing to provide verbal informed consent, or has a primary caregiver willing to provide proxy consent

- For healthcare workers:

- Staff members of the Family Health Team at the selected clusters
- Involved in delivering or supervising palliative care services during the study period
- For the qualitative part: Participated in the DINKNESH App implementation process and is willing to participate in a Focus Group Discussion (FGD)

Exclusion Criteria

- For patients

- Patients whose clinical condition prevents both self-participation and proxy participation in the assessment process
- Patients already formally identified and referred for palliative care prior to the study period

- For healthcare workers:

- Staff members planning to be absent for more than 1 day during the six-week active study period

- Healthworker not present during the training session

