The findings of this study will be submitted and presented to Addis Ababa University. The results will also be conveyed to the health office accountable, stakeholders, and health centers. An effort would be made to present it at various seminars, research conferences, and workshops. Finally, an attempt will be made to publish it in high impact journals. The study findings will be given to the Addis Ababa Health Bureau, as well as other relevant stakeholders.

9. Work Plan

[illegible]

[illegible]

Table 1: Work Plan

11. Budget Plan

No	Expenses	Measurement in Units/No.	Unit Price (ETB)	Total (ETB)
I. LOGISTICS + PERSONNEL COSTS FOR TRAINING				
1.	Compensation for Trainers	4 Trainers	1500/person/day For 3 days	18,000
2.	Venue + Daily Refreshments & Catering	24 HCW - 2HCW per health center - 24 HCW for 2 days and - 12 HCW for 3 days 4 trainer Total = 28 People - 28 people for 2 days	900/person/day For 3 days	64,800

		- 16 people for the 3rd day		
3.	Compensation for Trainee	24 HCW 2HCW per health center 24 HCW for 2 days and 12 HCW for day 3	600/person /day For 2 days - for 24 people 600/person /3rd day for 12 people	36,000
4.	Stationary(Photocopying & Tool Printing) and Supplies	Patient Consents,and other Notebooks, Pens, Batteries, Audio Recording	-	5,000
5.	Tablets	2 * 6 Tablets = 12 Tablets (2 Tablets per Health center)	- (will use existing DINKNES H tablets)	-
6.	Software Support Team Compensation	2 Team Members	For 3 months	12,000
II. DATA COLLECTION				

7.	SIM Card Purchase	12 SIM Cards	100/per SIM Card	1,200
8.	Internet Package for 2 months	12 Packages	400/per month For 2 months	9600
9.	Local Transportation (PI Supervision)	5 * 6 HC (Every 2 weeks in between monitoring) = 30 Trip within 2 months - Intervention Group	200/trip For 2 months	12,000
		5 * 6 HC (Every 2 weeks - in between monitoring) = 30 Trip within 2 months - Control Group	200/trip For 2 months	
10.	Local Transportation (Data Collector/ Quantitative)	9 * 6 Trips (Weekly Data Collection)= 54 trip within 2 months - Intervention Group	200 /trip For 2 months	21,600
		9* 6 Trips(Weekly data collection) = 54 Trip within 2 months - Control Group	200/trip For 2 months	

11.	Local transportation for X amount of indepth interview in identified patient houses for PI and Qualitative Data collector	2* X Trips	- For 1 month	5,000
12.	Data Collector/ Facilitator Payment	Quantitative Data collection+ Qualitative Data Collection for 2 month	5000/month For 2 months	10,000

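### The cluster is a health centre in sections 6.1 and 6.5 but two Family Health Teams in section 6.4, so the primary denominator is ambiguous and the choice of teams is not fixed before allocation

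*Protocol*

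**What the plan says.** The health centre is the cluster in two sections of the protocol. Section 6.1 says "12 eligible health centers are selected to serve as the study clusters". Section 6.5 says "In the first stage, the clusters are health centers within Addis Ababa that have palliative care services through Family Health Teams", and then that "these facilities will be randomly allocated to either the intervention or control group".

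Section 6.4 differs: "Each cluster is defined as two Family Health Team (FHT". It expects two teams to see about 120 chronic patients in six weeks. The design effect of 4.57, the 720 patients per arm and the total of 1,440 all rest on that figure.

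The population counted also varies by section:

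- Section 6.3.2 (patient inclusion criteria): patients must be "receiving home-based follow-up care from a participating Family Health Team within the catchment area of a selected study cluster".
- Section 6.5: the denominator is "all patients currently diagnosed with a chronic illness and receiving follow-up home-visit care from the Family Health Teams" in the catchment of the selected cluster. The word participating does not appear there.
- Section 6.8: the number identified is divided by all chronic patient encounters in the cluster.

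The Budget Plan provides for two health workers per centre in both arms and, for the six intervention centres, "2 * 6 Tablets = 12 Tablets (2 Tablets per Health center". Among the health worker exclusions in section 6.3.2 is "Healthworker not present during the training session". The protocol does not say how many teams a centre has, how or when two are chosen, or what happens to the patients of an excluded worker.

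**The concern.** The cluster definition decides who is in the primary denominator, and the two definitions can give different answers.

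If the cluster is the whole centre and the centre has more than two teams, sections 6.5 and 6.8 as written count patients whose team has no tablet. Those patients could not have been identified with the app, so the intervention proportion is pulled towards the control level while the sample size still assumes 15%.

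If the cluster is two teams within the centre, someone has to choose them. The concealment described in section 6.5 covers the allocation of facilities, not the choice of teams inside them. A choice made once the centre's arm is known could favour keener or better-equipped teams in the app arm. Adjustment for clustering would not remove that bias.

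The training exclusion adds a smaller gap. Excluding a worker without saying where that worker's patients go leaves open whether all eligible patients of a randomised cluster are analysed.

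**Working it through.** **The protocol's figure.** Inputs from section 6.4: p1 = 0.05, p2 = 0.15, z values 1.96 and 1.04, ICC 0.03, m = 120.

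- Unadjusted n per arm = (1.96 + 1.04)² × (0.05 × 0.95 + 0.15 × 0.85) / 0.10² = 9 × 0.175 / 0.01 = 157.5
- Design effect = 1 + 119 × 0.03 = 4.57
- n per arm = 157.5 × 4.57 = 719.8, and 719.8 / 120 = 5.998, so 6 clusters per arm and 1,440 in total

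The stated figures reproduce. They hold when the analysed cluster is two app-using teams with about 120 patients.

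**Counting the whole centre.** Assumptions, because the documents do not give these values: F teams per centre; 60 patients per team (120 / 2); two teams use the app and reach 15%; the other teams stay at 5%; ICC remains 0.03; 6 clusters per arm.

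- Intervention proportion: p2(F) = [2 × 0.15 + (F − 2) × 0.05] / F
- Cluster size m = 60F; design effect DE = 1 + (m − 1) × 0.03
- Effective n per arm = 6m / DE
- SE = √{[0.05 × 0.95 + p2(F)(1 − p2(F))] / effective n}
- Ratio = (p2(F) − 0.05) / SE
- Power by the protocol's normal approximation = Φ(ratio − 1.96)

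| Teams F | m | p2(F) | DE | Effective n | SE | Ratio | Power, normal | Power, t with 10 df |
|---|---|---|---|---|---|---|---|---|
| 2 | 120 | 15.0% | 4.57 | 157.6 | 0.0333 | 3.00 | 85% | 77% |
| 3 | 180 | 11.7% | 6.37 | 169.5 | 0.0298 | 2.24 | 61% | 52% |
| 4 | 240 | 10.0% | 8.17 | 176.3 | 0.0279 | 1.79 | 43% | 37% |

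The last column uses the non-central t distribution with 12 − 2 = 10 degrees of freedom and the ratio as non-centrality. The gap between 85% and 77% at two teams comes from the choice of test and has nothing to do with the cluster definition. The effect of the definition is read down a column.

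The loss is due to dilution. If all teams had the app (p2 = 15% throughout), the normal approximation would give 87.5% at three teams and 88.8% at four. The 5% assumed for teams without the app is the milder case: section 6.5 counts an intervention-arm identification only when it is made with the app, so read literally those teams would contribute none.

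**Selection of teams.** No arithmetic applies. The bias would depend on how the teams were chosen, and the protocol gives no rule.

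**Patients of a worker who misses training.** Suppose 10% of the two teams' patients are seen by someone not using the app. If they are kept, p2 = 0.9 × 0.15 + 0.1 × 0.05 = 14% and power by the normal approximation is 79%. If they are left out, m = 108 and power is 84%, but part of the randomised cluster is then missing.

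**The case against.** The strongest reply is that the sections fit together: the centre is sampled and randomised, two of its teams take part, and the two workers and two tablets per centre match that. The participating-team criterion in section 6.3.2 would then make patients of other teams ineligible, and the wide wording in section 6.5 would describe consecutive inclusion subject to that criterion. This is plausible and probably what was intended. It does not settle the matter. Sections 6.5 and 6.8 still state a wider denominator, and no section fixes the participating teams before allocation.

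It is also fair to say that the power figures depend on an assumed number of teams, and that the sample size contains no arithmetic error on this point. Both are accepted.

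Two stronger readings are tempting, and the text does not support them:

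- A reader might infer that patients exposed to the app are dropped. The training exclusion sits in the health worker list, and no section removes an excluded worker's patients. A worker who missed training would ordinarily not be using the app, so those patients would be mostly unexposed.
- A reader might infer that the training exclusion acts after allocation and differently by arm, because the budget gives 12 of 24 workers a third training day and 12 is one arm's number (6 × 2). The row suggests that allocation is known before training ends. It does not name the arm or tie third-day attendance to eligibility. Section 6.2 describes one initial session for both arms, and the exclusion refers to a single session. A differential exclusion is possible but not shown.

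**Conclusion.** The inconsistency is real and reaches the primary outcome. The centre is randomised, the sample size is built on two teams, and the denominator is worded for the whole centre in sections 6.5 and 6.8 but for participating teams in section 6.3.2. The plan is therefore open either to dilution (all teams counted) or to selection after allocation (two teams counted but not fixed beforehand).

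The size of the dilution cannot be derived from the documents. On the assumptions shown, power by the protocol's method falls from 85% to 61% with three teams per centre and 43% with four. If no centre has more than two teams, neither problem arises and only the wording needs correcting. The size of any selection bias cannot be quantified. On training, the sound point is limited: the protocol does not say what becomes of an excluded worker's patients. The correction is cheap and should be made before allocation, since a later analysis plan cannot restore a team choice made with the arm known.

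**What to change.** State once, and use throughout, that the health centre is the unit of randomisation and that two Family Health Teams per centre participate. Select those teams, preferably at random, and list them with their workers before the centres are allocated. A list completed before allocation would be enough to prevent selection by arm; a random draw also makes the teams representative of the centre.

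In sections 6.3.2, 6.5 and 6.8, use the eligible patients of those two teams as the single population for numerator and denominator, in both arms. Add that these patients stay in the analysis in their allocated arm even if a listed worker misses training.

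The cost is protocol wording and one selection step per centre before allocation. The sample size needs no change on this account. The downside is some dilution from patients of untrained workers: slight if few are affected, and from 85% to 79% power if they make up 10% of a cluster.
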